A clinical laboratory abnormality should be documented as an adverse event. Any adverse event that results in hospitalization or prolonged hospitalization should be documented and reported as a serious adverse event unless specifically instructed otherwise in this protocol. Any condition responsible for surgery should be documented as an adverse event if the condition meets the criteria for an adverse event. All unresolved adverse events should be followed by the investigator until the events are resolved, the subject is lost to follow-up, or the adverse event is otherwise explained

Serious Adverse Event

Adverse events are classified as serious or non-serious. A *serious adverse event* is any AE that is:

- fatal
- life-threatening
- requires or prolongs hospital stay
- results in persistent or significant disability or incapacity
- a congenital anomaly or birth defect
- an important medical event

Important medical events are those that may not be immediately life threatening but are clearly of major clinical significance. They may jeopardize the subject and may require intervention to prevent one of the other serious outcomes noted above. All adverse events that do not meet any of the criteria for serious should be regarded as *non-serious adverse events*. Serious adverse events that are still ongoing at the end of the study period must be followed up to determine the final outcome. Any serious adverse event that occurs after the study period and is considered possibly related to the study treatment or study participation should be recorded and reported immediately.

Adverse Event Reporting Period

The study period during which adverse events must be reported is normally defined as the period from the initiation of any study procedures to the end of the study treatment follow-up. For this study, the study treatment follow-up is defined as approximately 20 weeks following the last administration of study treatment.

Stopping Rules

Infusion Stopping Rules

Study treatment infusion will be stopped if a least one of the following events occur:

- 1. Allergic reaction as evidenced by severe dyspnea, bronchospasm, or hypoxia after the product has been administered intravenously.
- 2. Patient verbally decline the treatment at any moment prior, or during the infusion.
- 3. Hyperpyrexia develops after infusion administration begins (core body temperature greater than or equal to 104°F).
- 4. Principal Investigator may stop the infusion at any time, based upon PI's discretion.
- 5. Malignant Hypertension (180/120 mm/Hg)

Confidential

6. Sudden Severe Hypotension (30-40 mm/Hg drop from pre-infusion level)

If an infusion is stopped for a subject due to an adverse event or serious adverse event, including but not limited to hypersensitivity reaction/anaphylaxis, no additional study treatment will be given to the study participant who develops the event. Although, the study participant will not receive the investigational product, he or she must be followed for safety purposes according to the protocol.

Study Stopping Rules

This Clinical Trial will stop if any of the following events are present:

- 1. Subject's Death.
- 2. Occurrence of any thromboembolic event during or after HB-adMSCs administrations (up to 72 hours).
- 3. Any cerebrovascular ischemia or seizure event occurring within 72 hours after any of the investigational product administrations.
- 4. Any Serious Adverse Events determined to be related to the following:
 - When there is one CTCAE.v5 grade 4 or 5 AE, irrespective of attribution.
 - Either any CTCAE Grade 2 adverse event that persists for more than two weeks, or any Grade 3 adverse event, that occurs within 72 hours after product administration.

Should the study participant discontinue study treatment he/she will be followed for safety according to the protocol safety monitoring plan. The study participant will receive follow up communication to ascertain the outcome until resolved fully. All will be documented as per protocol.

Statistical Methods

Sample size consists of up to 24 subjects who have been diagnosed with Parkinson's disease. All data collected from subjects who are enrolled and received the investigational product will be analyzed. The incidence of Adverse Events and Serious Adverse Events will be recorded and reported. Efficacy will be measured by improvement of subject's signs and symptoms associated with Parkinson's disease. Interim analysis of all safety and efficacy data may be performed at any time deemed appropriate by the Sponsor. Although, the subject's data may be analyzed at any time, a data analysis of all available data will be conducted when a least 10 subjects in each group have completed Week 24. Data may be analyzed for internal informational purposes, reports, presentations, and manuscripts.

A repeat measure mixed model will be used to assess within-subject changes from baseline. correction for multiple comparisons will be employed for post-hoc comparisons. Parkinson's assessment scores (i.e., MDS-UPDRS) at screening and infusion 1 (before treatment) will be averaged and treated as a baseline. Averaging is performed to minimize sources of variance (i.e., patient condition, assessors) and particularly to establish a reliable baseline from which to establish changes.

Data Handling Case Report Forms (CRF)

As used in this protocol, the term CRF should be understood to refer to either a paper form or an electronic data record or both. Reports received by the site, or from the central laboratory should be printed, retained as source documentation and signed by the principal investigator, indicating which values are considered clinically significant and to be reported as AEs if applicable.

Source data is all information, original records of clinical findings, observations, or other activities in a clinical trial necessary for the reconstruction and evaluation of the trial. Source data are contained in source documents

Changes in the Conduct of the Clinical Trial Protocol Amendments

Any change to the protocol will need to have a protocol amendment submitted to the IND, and FDA and IRB must agree prior to proceeding.

Deviations from the Protocol

Deviations from the protocol should not occur. If safety deviations occur, the principal investigator must inform the Monitor, and the implications of the deviations must be reviewed and discussed. Any deviation must be documented in the protocol deviation log. In addition, each deviation must include a description of the deviation, the relevant dates (start and stop), and the action taken. All deviation reports and supporting documents must be kept in the Investigator Site File and in the Trial Master File.

Premature Clinical Trial Termination

Both the Study Investigator and Sponsor have the right to terminate the clinical trial at any time. Should this become necessary, the procedures will be agreed upon after consultation between the two parties. In terminating the clinical trial, the Sponsor and the Study Investigator will ensure that adequate consideration is given to the protection of the best interests of the study participants. Regulatory authorities and IRB will be informed.

In addition, the Sponsor reserves the right to terminate the participation of any clinical trial site. Conditions that may warrant termination include, but are not limited to:

- Insufficient adherence to protocol requirements
- Failure to enter patients at an acceptable rate

Reporting and Publication

Neither the complete nor any part of the results of the study carried out under this protocol, nor any of the information provided by the sponsor for the purposes of performing the study, will be published or passed on to any third party without the consent of the study sponsor.

Any investigator involved with this study is obligated to provide the sponsor with complete test results and all data derived from the study.

Archiving

Investigator File

The study investigator is responsible for maintaining all the records (protocol and protocol amendments, completed source and case report documents, signed informed consent forms, relevant communications and all other supporting documents) which allow to conduct the clinical trial at the site in compliance with ICH-GCP. The study site should retain such documents until at least 2 years after the last approval of a marketing application or at least 2 years after the formal discontinuation of clinical development of the investigational product. These documents should be retained for a longer period if required by the applicable regulatory requirements in which the study is being conducted. Patient identification codes (patient names and corresponding study numbers) will be retained for this same period of time. The Investigator must contact Sponsor prior to disposing of any study records.

Trial Master File

The Sponsor will archive the Trial Master File in accordance with ICH-GCP and applicable regulatory requirements.

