Clinical assessments of disease activity will take place during the following visits:

- Visit 1 Screening
- Visit 2 Infusion 1 (**Baseline**)
- Visit 3 Infusion 2
- Visit 4 Infusion 3
- Visit 5 Infusion 4
- Visit 6 Infusion 5
- Visit 7 Infusion 6
- Visit 8 Safety Follow Up
- Visit 9 End of Study

Blood samples for safety assessments will be collected in as follows:

- Visit 1 Screening: after informed consent has been obtained, blood samples should be collected from a vein of the study's participant arm, these lab results will help assess the subject's eligibility.
- Visit 2 Infusion 1, (**Baseline**): safety laboratory samples should be collected from a vein of the study participant in order to set a start point of comparing with the laboratory results to obtain in the following visits. Although, laboratory samples are a requirement of this visit, in certain situations this requirement will be avoided, and the laboratory results obtained during Visit 1 Screening will be used as a Baseline. See some of these situations below:
 - Period of time between Visit 1 Screening and Visit 2 Infusion 1 (Baseline) is less than 10 days.
 - The study participant had no change in medical history or concomitant medications since Visit 1 Screening.
 - No changes in physical examination are identified by principal investigator during Visit 2 – Infusion 1, (Baseline).
- Visit 6 Infusion 5: safety laboratory samples should be collected from a vein of the study's participant arm during this visit.
- Visit 9 End of Study: safety laboratory samples should be collected from a vein of the study's participant arm during this visit.

For study participants who do not complete the study trial, a safety follow-up visit will be scheduled as follows:

- For subjects who did not receive any the investigational product, a safety follow-up visit, or Early termination visit (ETV) will be scheduled as soon as possible, but not later than 30 days after the last visit.
- For subjects who received at least one dose of the investigational product, a safety follow-up visit will be scheduled approximately 30 days after that single dose.
- For subjects who received more than one dose of the investigational product, a safety follow-up visit will be scheduled after the last investigational product administration.

Withdrawal Criteria

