In addition to the study participant's right to withdraw from the clinical trial at any time for any reason, without the need to justify their decision, DSMB and principal investigator have the right to withdraw study participants from the clinical trial if any of the following circumstances are present:

- Lost to follow-up (every effort should be made to contact study participants; these attempts to contact study participants should be documented). Appendices Attempts to contact study participants.
- A serious adverse event which, in the opinion of the DSMB and the principal investigator, requires the withdrawal of the study participant.

Study participants discontinued from the clinical trial who received at least one infusion (HB-adMSCs or placebo) will be invited to a Safety Follow-up visit approximately 30 days after that single infusion. During this visit, study staff should record the reason of discontinuation.

Any withdrawal must be documented in the source documents and electronic case report forms, if the reason for the discontinuation is an adverse event or serious adverse event, the event must be followed until resolution by the principal investigator.

The Sponsor may temporarily or permanently discontinue the clinical trial at any time for safety, ethical, compliance or other reasons. Study's principal investigator and regulatory authorities will be notified about this decision and the reason of it.

Selection of Clinical Trial Population

Clinical Trial Population

This clinical trial is designed to include adult male and female outpatients with Parkinson's disease. Study participants who fulfil all of the inclusion criteria and none of the exclusion criteria are eligible for participation in the clinical trial. See below eligibility criteria: **Eligibility Criteria**

Inclusion Criteria

A study participant will be eligible for inclusion in this study only if all of the following criteria apply:

- 1. Male and female participants 18 75 years of age.
- 2. Study participant must have been diagnosed with early and/or moderate Parkinson's disease at least 6 months before study participation.
- 3. Study participants must have previously banked their mesenchymal stem cells with Hope Biosciences.
- 4. Study participants should be able to read, understand and to provide written consent.
- 5. Voluntarily signed informed consent obtained before any clinical-trial related procedures are performed.

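### Dosed participants who leave the trial have one explicitly scheduled safety visit, about 30 days after an infusion, while adverse-event reporting runs to about 20 weeks after the last infusion

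*Protocol*

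**What the plan says.** Two places in the protocol set the exit visit for participants who have been dosed and then leave.

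- Withdrawal Criteria: a participant with at least one infusion "will be invited to a Safety Follow-up visit approximately 30 days after that single infusion".
- Investigational Plan, for non-completers: after at least one dose, "a safety follow-up visit will be scheduled approximately 30 days after that single dose"; after more than one dose, "a safety follow-up visit will be scheduled after the last investigational product administration", with no interval.

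The Adverse Event Reporting Period section sets a longer horizon for reporting: "the study treatment follow-up is defined as approximately 20 weeks following the last administration of study treatment". The Investigational Plan and Trial Procedures also give a 20-week safety follow-up.

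Other provisions bear on people who leave or stop treatment:

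- Adverse Event: "All unresolved adverse events should be followed by the investigator until the events are resolved". Withdrawal Criteria likewise has an event that caused the discontinuation followed to resolution.
- Serious Adverse Event: "Any serious adverse event that occurs after the study period and is considered possibly related to the study treatment" or participation is to be recorded and reported.
- Study Stopping Rules: a participant who discontinues study treatment is "followed for safety according to the protocol safety monitoring plan" and receives "follow up communication to ascertain the outcome until resolved fully".

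The Week 42 visit is described as being for participants still active in the study.

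In the SAP, the objectives and endpoints table counts SAEs over 52 weeks. It also lists adverse events of special interest, without a window. Section 4 keeps everyone with at least one dose in the Safety analysis set.

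**The concern.** The reporting period covers about 20 weeks after the last dose, but the one contact explicitly planned for a leaver falls early in it. The remaining provisions either follow events that are already known or accept a report if one arrives. None of them, as printed, goes looking for a new event in someone who has left.

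SAEs and adverse events of special interest are among the primary endpoints, under a heading that runs from baseline to Week 52. SAP 8.1 reports the number and percentage of subjects with an event, and every dosed participant is in the denominator. A leaver whose later event goes unreported is therefore tabulated as event-free. With 12 per arm, and assuming that all 12 are dosed, one such participant changes an arm's incidence by 1/12, about 8 percentage points. That shows how sensitive small arms are; it does not estimate what will happen.

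**Working it through.** **The plan's own figure.** For a completer, the last infusion is at Week 32 and End of Study is at Week 52. 52 − 32 = 20 weeks = 20 × 7 = 140 days. This reproduces the stated 20-week follow-up.

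**Coverage for a leaver.** Inputs: exit visit at day 30 (Withdrawal Criteria) and reporting to day 140 (Adverse Event Reporting Period). Visit windows of ±7 days are ignored.

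- Covered: 30/140 = 21.4%.
- Not covered: 140 − 30 = 110 days, or 78.6%.

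This is the maximum. It applies to someone who leaves within about 30 days of an infusion. Later leavers have been seen for longer:

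- Leaving at the next infusion visit after an 8-week interval: 140 − 56 = 84 days.
- Leaving at Week 42 after Infusion 6: (42 − 32) × 7 = 70 days seen, and 140 − 70 = 70 days not seen.

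**How much of the 52-week gap comes from the exit rule.** Assume a visit 30 days after the last infusion, given at Week w. Observation ends at day 7w + 30. Days missing from 52 weeks (364 days) are 364 − (7w + 30). A call at Week w + 20 recovers 140 − 30 = 110 of them.

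| Last infusion | Missing with 30-day visit only | Share recovered by a 20-week call | Call at | Still missing |
|---|---|---|---|---|
| Week 0 | 334 | 110/334 = 33% | Week 20 | 224 |
| Week 4 | 306 | 110/306 = 36% | Week 24 | 196 |
| Week 8 | 278 | 110/278 = 40% | Week 28 | 168 |
| Week 16 | 222 | 110/222 = 50% | Week 36 | 112 |
| Week 24 | 166 | 110/166 = 66% | Week 44 | 56 |
| Week 32 | 110 | 110/110 = 100% | Week 52 | 0 |

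The last column is due to leaving early, not to the exit rule.

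**Which counts are affected.** SAP 8.1 closes the treatment-emergent window 3 days after the last infusion. A visit at day 30 already covers that, so the treatment-emergent count does not change. The exposure is in the SAE count and the special-interest events.

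**What other scheduled contacts exist.** In Table 3, adverse-event assessment is tied to Visits 2 to 9, and the 24-hour telephone calls follow infusions only. Neither gives a leaver a contact after the exit visit.

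**The case against.** The strongest reply is that a reporting window is not a contact schedule. One says which events count and the other says when someone is seen, so 30 days and 20 weeks can both apply without contradiction. That stands. A reader might infer that the protocol contradicts itself, but the documents show only that no later active contact is written down.

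Second, the sentence under Study Stopping Rules is not limited to people who stop infusions but stay in the trial. Anyone who leaves before Infusion 6 has also discontinued treatment, so the safety monitoring plan may cover them. The sentence's position under the stopping rules leaves its reach open, and the plan itself cannot be read here. A reader might infer that leavers are dropped from safety follow-up; the documents do not settle that either way.

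Third, the 30-day interval is explicit only for a single infusion or dose. After several doses, the Investigational Plan gives no interval, and 30 days after the last infusion is an inference from Withdrawal Criteria. For those participants the firmer finding is that the timing is unspecified. A 110-day gap for every dosed leaver is not established.

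Fourth, few people are affected. Those lost to follow-up cannot be called, and an event that caused a withdrawal is followed anyway. This also stands, although someone withdrawn because of an SAE may be willing to be contacted, and for that person new events are not actively sought.

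**Conclusion.** The point holds as a minor gap in planned ascertainment, not as a proven error. As printed, the protocol explicitly schedules one contact for a dosed leaver. Up to 110 of the 140 reporting days follow it with no scheduled contact, falling to 84 or 70 days in the later-leaving cases worked above.

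This rests on two assumptions: that the exit visit after several doses is meant to be about 30 days after the last one, and that the safety monitoring plan does not already schedule contacts for leavers. If it does, the gap shrinks or disappears.

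A reader might go further and infer that the trial's safety results will be biased. The documents do not support that. They give no dropout rate, no split by arm and no late event rate, so neither the size nor the direction of any bias can be computed. The number of leavers who would accept further contact is probably small in a trial of 24.

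**What to change.** In the Investigational Plan and Withdrawal Criteria, use one rule for every dosed participant who leaves, whatever the number of infusions:

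- a visit about 30 days after the last infusion, or as soon as possible if that day has passed;
- one telephone contact about 20 weeks after the last infusion to ask about adverse events and SAEs, subject to consent.

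Under Study Stopping Rules, state whether safety follow-up under the monitoring plan applies to people who leave the trial as well as to those who stop infusions.

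Optionally, show observed follow-up time beside the SAE and special-interest counts, so that unequal observation is visible. The SAP text shows no such measure, although its display lists are not available to check.

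The cost is a wording change and one extra call per leaver. Some will decline, and the call will not reach those lost to follow-up. It brings contact into line with the protocol's own 20 weeks but does not restore 52 weeks for people who leave early.

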Weight	•	•	•	•	•	•	•	•	•										
Height	•																		
Laboratory Samples ¹	•	•				•			•										
Physical Examination	•	•	•	•	•	•	•	•	•										
Parkinson's Disease Assessments ²	•	•	•	•	•	•	•	•	•										
Study Treatments Administration		•	•	•	•	•	•												
24 hours Telephone Encounter		•	•	•	•	•	•												
Video Documentation	•	•				•			•										
AE and SAE assessments		•	•	•	•	•	•	•	•										

2. Parkinson's disease Assessments – MDS-UPDRS, VAS pain and muscle spasms, Neuro-Quality of Life Assessments, Parkinson's disease fatigue scale (PFS-16) and Parkinson's disease Questionnaire (PDQ-39).

Study Visits 1 to 9.

Visit 1 – Screening.

At the Screening Visit (Visit 1), study participants' information will be collected by study's delegated personnel for evaluation of trial eligibility. The following information is required to determine eligibility:

- Signing Informed Consent Form (prior to any trial-related activities).
- Collection of demographic information, such as age, race, ethnicity, date of birth, gender and relevant medical and surgical history.
- Collection of Medical History and concomitant medications, including relevant information about the past and present health of study participants.
- Inclusion and Exclusion criteria evaluation.
- Measurement of vital signs including respiratory rate, body temperature, blood pressure, pulse rate, oxygen saturation, weight and height.
- Collection of laboratory samples, including Comprehensive Metabolic Panel (CMP), Complete Blood Count (CBC), Coagulation Panel and Urine pregnancy test if female of childbearing potential.
- Physical examination by Principal Investigator, including clinical assessments such as MDS-Unified Parkinson's Disease Rating Scale and other assessments included in Table 3.
- Completion of neuro-quality of life questionnaire by study's participant and handwriting assessments.
- A video documenting study participant walking and standing from sitting will be recorded during this visit.

Within 28 days of the Visit 1 - Screening, the principal investigator must make a decision to determine participant's eligibility. Once, the eligibility of the subject has been confirmed by the principal investigator, the randomization process will be conducted.

Visit 2 – Infusion 1 (Baseline)

The following procedures are required during this visit:

- Reconfirm eligibility criteria.
- Update medical history and concomitant medications if any change occurred since last visit.

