- Measure vital signs including respiratory rate, body temperature, blood pressure, pulse rate, oxygen saturation and weight.
- Collect laboratory samples, including Comprehensive Metabolic Panel (CMP), Complete Blood Count (CBC), Coagulation Panel and Urine pregnancy test if female of childbearing potential.
- Physical examination by Principal Investigator, including clinical assessments such as MDS-Unified Parkinson's Disease Rating Scale and other assessments included in Table 3.
- Completion of neuro-quality of life questionnaire by study participant and handwriting assessments.
- Investigational product administration by delegated study personnel. HB-adMSCs or Placebo should only be administered intravenously, with a dosing rate of 4-5ml/min and a vital sign monitoring of two hours post-drug exposure. Monitoring time may be prolonged if decided by principal investigator. Vital signs must be monitored as follows:

- A video documenting study participant walking and standing from sitting will be recorded during this visit. However, if the period of time between Visit 1 Screening and Visit 2 Infusion 1 (Baseline) is less than 10 days, the video does not need to be repeated.
- 24 hours after administration of the investigational product, study participants will be contacted by telephone call to assess the incidence of adverse events.

Visit 3, 4, 5 6, and 7 – Infusions 2, 3, 4, 5 and 6

- Update medical history and concomitant medications if any change occurred since last visit.
- Measure vital signs including respiratory rate, body temperature, blood pressure, pulse rate, oxygen saturation and weight.
- Physical examination by Principal Investigator, including clinical assessments such as MDS-Unified Parkinson's Disease Rating Scale and other assessments included in Table 3.
- Completion of neuro-quality of life questionnaire by study participant and handwriting assessments.
- Collection of laboratory samples, including Comprehensive Metabolic Panel (CMP), Complete Blood Count (CBC), Coagulation Panel and Urine pregnancy test if female of childbearing potential (only during Visit 6, Infusion 5)

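### The last scheduled contact after each infusion is a 24-hour call, so the final 48 of the 72 hours used by three trial-stopping criteria are not actively asked about until the next clinic visit

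*Protocol*

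**What the plan says.** **Contacts after a dose.** In the protocol's Visit 2 procedures and in those for Visits 3 to 7, vital signs are monitored for two hours after exposure, longer if the investigator wishes. Then: "24 hours after administration of the investigational product, study participants will be contacted by telephone call to assess the incidence of adverse events". Table 3 has one telephone row, "24 hours Telephone Encounter", marked at Visits 2 to 7. It also has a row "AE and SAE assessments" at Visits 2 to 9, which does not say whether the questions come before or after dosing. No contact is scheduled between the 24-hour call and the next clinic visit.

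**Trial-stopping criteria.** Under Study Stopping Rules:

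- Rule 2: "Occurrence of any thromboembolic event during or after HB-adMSCs administrations (up to 72 hours".
- Rule 3: "Any cerebrovascular ischemia or seizure event occurring within 72 hours after any of the investigational product administrations".
- Rule 4, Grade 3 clause: "or any Grade 3 adverse event, that occurs within 72 hours after product administration". The stem of rule 4 begins "Any Serious Adverse Events determined to be", so this clause may be confined to serious events. Rules 2 and 3 carry no such limit.

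**Early stoppers.** The Investigational Plan gives participants who stop after a single dose a safety visit about 30 days after it. For those who stop after more than one dose it states no interval.

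**The concern.** The sponsor chose 72 hours as the period in which certain events halt the whole trial, but scheduled active questioning only at 24 hours. A participant with symptoms on day 2 or 3 who does not contact the site is first asked at the next visit, weeks later.

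Two things are at stake. The first is the safety of other participants. These rules act on the trial, not only on the affected person, and others can go on being infused until the trigger is known. The second is dating. Rules 2 and 3 and the Grade 3 clause turn on whether onset fell within 72 hours. For an event that led to no medical care, that would have to be recalled after 4 to 10 weeks.

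**Working it through.** The plan states no figure for this delay, so there is none to reproduce. The check is calendar arithmetic.

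**Inputs (protocol).** Infusions at weeks 0, 4, 8, 16, 24 and 32, and the next visit after infusion 6 at week 42 (Study Summary). Call at 24 hours (visit procedures). Window of 72 hours, or 3 days (Study Stopping Rules). Visit windows of ±7 days (Table 3). 24 participants, 12 per arm (Investigational Product Assignment).

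**Unasked part of the window.** 72 − 24 = 48 hours, or 48/72 = two thirds.

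**Delay after the window closes.** (Next visit week − infusion week) × 7 − 3 days. The last column allows ±7 days on both visits, that is ±14 days on the gap.

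| Infusion | Week | Next visit, week | Gap, days | Nominal delay, days | With visit windows, days |
|---|---|---|---|---|---|
| 1 | 0 | 4 | 28 | 25 | 11 to 39 |
| 2 | 4 | 8 | 28 | 25 | 11 to 39 |
| 3 | 8 | 16 | 56 | 53 | 39 to 67 |
| 4 | 16 | 24 | 56 | 53 | 39 to 67 |
| 5 | 24 | 32 | 56 | 53 | 39 to 67 |
| 6 | 32 | 42 | 70 | 67 | 53 to 81 |

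The nominal mean is (25 + 25 + 53 + 53 + 53 + 67)/6 = 276/6 = 46 days. If week 0 is the fixed anchor, infusion 1 becomes 18 to 32 days; the overall range stays 11 to 81. The 4 to 8 weeks between doses given under Treatment Regimen agrees with the table for infusions 1 to 5: 28 − 3 = 25 and 56 − 3 = 53. For someone who stops after one dose, the delay is about 30 − 3 = 27 days.

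**Infusions concerned.** Delay of 25 days: 24 × 2 = 48. Delay of 53 days: 24 × 3 = 72. Delay of 67 days: 24 × 1 = 24. Total 144 at most. Rule 2 covers active infusions only, 12 × 6 = 72 at most. Rule 3 and the Grade 3 clause cover all 144.

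**Exposure of others meanwhile.** On nominal infusion days 0, 28, 56, 112, 168 and 224, one other participant can receive:

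- at most 1 infusion in a 25-day span;
- at most 2 in 53 days (three need 56);
- at most 3 in 67 days (days 0, 28 and 56).

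The minimum is 0 in each case. Visit windows loosen these limits: with week 4 at day 21, two infusions fit in 25 days, and with week 8 at day 56 − 7 = 49, three fit in 53. These are schedule limits, not estimates. Accrual, which decides how many participants are on treatment together, is not given.

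**With a call at 72 to 96 hours.** The delay becomes 0 to 24 hours, provided the call is answered and the participant mentions the event.

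**The case against.** The strongest reply is that 72 hours defines which events count, and nothing obliges the sponsor to schedule questioning across that window. Strokes, seizures and symptomatic clots usually bring people to medical care. Adverse events are reportable throughout follow-up and are to be recorded immediately. Hospitalization makes an event serious, unscheduled visits are available, and the adverse-event process provides for review by the medical monitor or the DSMB. Death and the Grade 4 or 5 clause have no 72-hour limit. Consent pages were removed from the review copy, and the plan cited in "he/she will be followed for safety according to the protocol safety monitoring plan" was not supplied. Either could contain an instruction to report at once, or further contacts.

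Much of this stands. It means the 25 to 67 days apply only to a symptomatic trigger starting between 24 and 72 hours that nobody reports. How often that would happen is not in the documents. A call would not find a silent thromboembolism either. But each visible safeguard acts only once the event is known, and the call is meant to make it known.

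Four stronger readings are tempting, and the documents do not support them:

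- **The stopping rules cannot work.** They can. Any trigger that becomes known, by whatever route, can be acted on.
- **The affected person would be dosed again with the event unseen.** At Visits 3 to 7 the history update, vital signs and physical examination, which includes neurological and mental status, are listed before dosing. An event would normally surface then.
- **Onset could be dated only by recall.** A treated event can be dated from medical records. Recall is the issue only for untreated events.
- **Treatment-emergent counts would be distorted.** SAP 8.1 treats events with missing dates as treatment-emergent. Only a wrongly recalled date after the last infusion could move an event across its 3-day cut-off, which is marginal.

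**Conclusion.** The point holds for scheduled contacts. Two thirds of the 72-hour window behind rules 2 and 3 and the Grade 3 clause of rule 4 falls after the last scheduled contact. Active questioning about those 48 hours waits a nominal 25 to 67 days after the window closes, or 11 to 81 days with visit windows. The consequence is narrow: a symptomatic trigger that goes unreported could leave the trial running, with others being infused, until the next visit. Its frequency is unknown.

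The conclusion assumes that the consent form and the safety monitoring plan, neither of which can be seen, add no scheduled contact. Even then, the weight of the Grade 3 clause depends on whether the stem of rule 4 limits it to serious events; rules 2 and 3 do not depend on that. This is a cheap improvement that the sponsor should make, not a failure of the safety plan.

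**What to change.** Keep the 24-hour call and all stopping criteria. Add to Table 3, to the Visit 2 procedures and to the Visit 3 to 7 procedures one scripted adverse-event call at 72 to 96 hours after each infusion. The script should ask about symptoms of the trigger events and record onset date and time. Repeat attempts should be specified if the call is unanswered. Because site staff are blinded, every participant gets the call in both arms.

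The cost is up to 24 × 6 = 144 short calls by existing staff, plus an amendment to Table 3 and two visit sections. Under Protocol Amendments, that needs submission to the IND and agreement from FDA and the IRB. No new visit or procedure is required.
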